## **Outcome status**

### *Definition of treatment failure:*

Patient whose baseline smear (or culture) was positive and remains or becomes positive again at 5 months or later during treatment. This definition excludes those patients who are diagnosed with RR-TB or MDR-TB during treatment.

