The principle of not adding a single drug to a failing regimen is well-known and the authors are well aware of this rule. The difference in this study is that all patients will be screened for Rifampicin susceptibility using Gene Xpert and any patient displaying Rifampicin resistance will be excluded. In addition, full susceptibility testing using MGIT, HAIN line probe assay and conventional culture will be conducted. Patients displaying multi drug resistance will be withdrawn from the study and referred for appropriate treatment at the provincial referral hospital which is within 10kms from trial site.

Moxifloxacin has been selected for use in this study due to its excellent safety profile and favourable outcomes in treating Tuberculosis. Several scientists in the field of TB research have recommended that further research on Moxifloxacin is needed to establish its ability to shorten the course of TB treatment.

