## 4.0 INCLUSION AND EXCLUSION CRITERIA

### 4.1 Inclusion

- 4.1.1 Adults  $\geq$  18 years of age
- 4.1.2 Previous history of anti-TB chemotherapy
- 4.1.3 HIV status: HIV infected and uninfected patients are allowed in the study:
  - 4.1.3.1 All patients must agree to HIV testing to confirm HIV status.
  - 4.1.3.2 Patients already on ARVs will be allowed in the study provided that the ART regimen is not contraindicated with any of the study agents (see 4.2.1 below).
  - 4.1.3.3 HIV infected patients at any CD4 count irrespective of ART commencement and duration will be included in the study
- 4.1.4 Smear positive
- 4.1.5 Rifampicin susceptible as determined by Gene Xpert at screening. Gene Xpert will be used to determine Rifampicin resistance, hence the study team will be made aware of resistance prior to study enrolment.
- 4.1.6 Karnofsky score  $\geq$  70
- 4.1.7 Female candidates of reproductive potential must agree to use two reliable methods of contraception while on study: a barrier method of contraception (condoms or cervical cap) together with another reliable form of contraceptive (condoms with a spermicidal agent, a diaphragm or cervical cap with spermicide, an Intrauterine Device (IUD), or hormone-based contraceptive)
- 4.1.8 A negative pregnancy test
- 4.1.9 Laboratory parameters done at, or  $\leq$  14 days prior to, screening:
  - Haemoglobin level of at least 7.0 g/dL
  - Serum aspartate transaminase (AST) and alanine transaminase (ALT) activity less than 3 times the upper limit of normal
  - Serum total bilirubin level less than 2.5 times upper limit of normal
  - Creatinine clearance (CrCl) level greater than 60 ml/min
  - Platelet count of at least  $50 \times 10^9$  cells/L
  - Serum potassium greater than 3.0 mmol/L

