## **Withdrawal from the study**

Patients withdrawn from study due to a protocol violation will be included in the safety database of the study. Patients withdrawn from study because their initial TB isolate is found to be MDR –TB will not be followed up further, unless required for patient safety (e.g. an adverse event present, in which case follow-up should occur as clinically indicated). Similarly, patients withdrawn from study because their initial cultures are negative do not need to be followed up further (unless there is an ongoing adverse event). Participation in the study is strictly voluntary. A participant has the right to withdraw from the study at any time for any reason. Patients who withdraw their consent will not have to undergo any follow up procedures.

This study will be reviewed by a Safety Monitoring Committee (SMC) that meets for scheduled reviews of studies every year. A full SMC review will include an efficacy review and a futility review for detecting a survival difference. A full review will be scheduled at least annually after opening to accrual or on a frequency determined by the SMC. For each full review, summaries provided to the SMC will be broken down by treatment arm. Participants' baseline demographic and health characteristics will be summarized. Review of study conduct will address site accrual, premature study discontinuations and their reasons (administrative or loss to follow-up), tracking of potential losses to follow-up, data completeness. The SMC will also review participants' safety data, frequency and causes of death, as well as incidence of TB recurrence.

In addition, quarterly internal reviews of patient charts, SAE reports and regulatory submissions will be conducted.

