## **9.3 Explanation on how the results of this study will be used**

Many published reports have questioned the effectiveness of the standard WHO retreatment regimen and, more importantly the potential for amplification of TB drug resistance. Despite the enormous patient and public health cost of drug resistant TB, there has been a lack of research effort directed at investigating alternate regimens aimed at optimising treatment outcomes among retreatment patients who are most at risk of developing acquired drug resistant TB. This study proposes to use a regimen that omits an injectable agent, enhances time to culture conversion thereby shortening duration of treatment, increasing adherence and completion rates and reducing the likelihood of acquiring drug resistance. The availability of new generation rapid diagnostic technologies offers a unique opportunity of providing a targeted retreatment approach without compromising the efficacy of second line agents used to treat drug resistant TB. The goal of global tuberculosis research and control efforts to date has been the development of shorter TB treatment regimens. Investigating a retreatment regimen that can shorten duration of therapy is central to enhancing programmatic outcomes and this study is commensurate with this goal. Treatment default is associated with length of treatment, thus shortening treatment duration could improve outcomes, and reduce labour and financial implications of national TB control programs especially in countries with a high TB incidence. This study will explore an alternate retreatment regimen suitable for a national TB control program in a TB-HIV endemic setting.

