##### Intention-to-treat population

This population consists of all participants enrolled and randomised to the intervention and control arms. Individuals who will be identified as ineligible for enrolment based on criteria pre-randomisation criteria will be excluded. Moreover, individuals with no post-randomisation visit and no data collected will be excluded.

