#### **6.7. Secondary objective 4**

*To compare the rates of treatment failure and recurrence of the intervention and control arm.*

This will be done by calculating the proportion of participants who do not have a negative culture result at end of treatment or who relapse post treatment in each of the two arms. The proportions will be compared these using the chi-square test or the Fisher's exact test.

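### The protocol's treatment-failure definition drops rifampicin or multidrug resistance diagnosed on treatment whatever the baseline isolate showed, and the SAP's failure endpoint does not match it

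*Protocol*

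**What the plan says.** **Failure, protocol.** Under Outcome status, failure is a positive baseline smear or culture that stays or turns positive at 5 months or later on treatment. The next sentence reads: "This definition excludes those patients who are diagnosed with RR-TB or MDR-TB during treatment". Neither the baseline isolate nor an alternative outcome category is mentioned.

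**Failure, SAP 6.7.** The analysed quantity is the "proportion of participants who do not have a negative culture result at end of treatment or who relapse post treatment". There is no exclusion for resistance. The intention-to-treat definition in SAP section 4 does not remove these patients either: "This population consists of all participants enrolled and randomised to the intervention and control arms". SAP section 5 ignores missing data as missing at random unless patterns suggest bias.

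**Entry.** Protocol 4.1.5 requires participants to be "Rifampicin susceptible as determined by Gene Xpert at screening".

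**Withdrawal.** Protocol 1.3 states: "Patients displaying multi drug resistance will be withdrawn from the study and referred for appropriate treatment at the provincial referral hospital". It gives no timing and names multidrug resistance only. Protocol 8.2.3 and the section on withdrawal from the study are narrower: "Patients withdrawn from study because their initial TB isolate is found to be MDR –TB will not be followed up further".

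**Purpose.** Objective 2.2.4 compares failure and recurrence between arms. Protocol 9.3 gives as part of the trial's rationale "increasing adherence and completion rates and reducing the likelihood of acquiring drug resistance".

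**The concern.** Because entry requires rifampicin susceptibility, RR-TB or MDR-TB first diagnosed on treatment has three possible sources: resistance missed at entry, reinfection, or resistance acquired on the assigned regimen. Leaving out the first is reasonable, since a regimen should not be blamed for resistance already present. The protocol rule does not separate the three, so it also leaves out the third.

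Acquired resistance is a post-randomisation event that the regimens may cause at different rates. The continuation phase is HRM in one arm and HR in the other. A failure comparison that drops patients because of such an event no longer compares the groups as randomised. It flatters the arm with more acquired resistance: it hides harm if that is the intervention arm, and benefit if it is the control arm. It also leaves out an event that protocol 9.3 says the trial hopes to reduce.

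**Working it through.** **1. One patient under each rule.** Take a patient with a susceptible baseline isolate who is culture-positive at month 5 with new rifampicin resistance and stays positive.

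| Rule | Classification |
|---|---|
| Protocol failure | Meets the first sentence, removed by the second: not a failure |
| Protocol cure | No negative result in the last month: not cured |
| SAP 6.7, end-of-treatment culture taken | No negative culture: an event |
| SAP 6.7, no end-of-treatment culture | An event if read literally; dropped if SAP section 5 is applied |

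The protocol gives this patient no outcome category. The SAP result depends on a missing-data choice that it does not settle.

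**2. Size, with assumed rates.** The documents give no rate of failure or of acquired resistance, so every rate here is an assumption. Let f be other failure and r be RR/MDR-TB diagnosed on treatment, all of it acquired. Control: f = 8%, r = 3%. Intervention: f = 5%, r = 1%.

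- Counted as failures, f + r: 8 + 3 = 11% v 5 + 1 = 6%, difference 5.0 points.
- Removed from numerator and denominator, f/(1 − r): 8/97 = 8.2% v 5/99 = 5.1%, difference 3.2 points.
- Removed from the numerator only (the protocol does not say which): 8% v 5%, difference 3.0 points.

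With both removed, (5.0 − 3.2)/5.0 = 36% of the difference is lost, about a third.

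If half of the on-treatment diagnoses were resistance missed at entry (assumed), those patients would properly be excluded. The corrected rates are (8 + 1.5)/98.5 = 9.6% v (5 + 0.5)/99.5 = 5.5%, a difference of 4.1 points against the protocol rule's 3.2. The distortion shrinks but does not vanish.

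**3. Can it change a conclusion?** Arm size comes from protocol 9.1: 75% v 60%, two-sided 0.05, 80% power. Uncorrected n = [1.96·√(2 × 0.675 × 0.325) + 0.842·√(0.75 × 0.25 + 0.60 × 0.40)]² / 0.15² = 152. With continuity correction, (n/4)·[1 + √(1 + 4/(n × 0.15))]² = 165 per arm, 330 in total. This reproduces the stated sample size.

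With 165 per arm, assumed counts and Fisher's exact test:

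| Assumed counts | Protocol rule | Counted as failures |
|---|---|---|
| 10 other failures per arm; 5 RR/MDR in one arm only | 10/160 = 6.2% v 10/165 = 6.1%, p = 1.00 | 15/165 = 9.1% v 10/165 = 6.1%, p = 0.41 |
| Intervention 6 other + 4 RR/MDR; control 16 other + 0 | 6/161 = 3.7% v 16/165 = 9.7%, p = 0.045 | 10/165 = 6.1% v 16/165 = 9.7%, p = 0.31 |

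In the second row, four cases of resistance in the intervention arm decide whether its failure rate appears significantly lower.

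**4. Primary endpoint.** Culture conversion is touched only through missing cultures. If 3% or 10% of each arm were lost (assumed), continuity-corrected power would fall from 80% to about 79% or 75%.

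**The case against.** The strongest reply is that the planned analysis does not use the protocol exclusion. SAP 6.7 has none, the intention-to-treat population keeps these patients, and a literal reading counts anyone without a negative end-of-treatment culture. On that reading the 5.0-point difference in the illustration is preserved, provided the patients with resistance have no such negative culture. This stands. The bias arises only if the protocol definition is applied, or if patients without that culture are ignored as missing. What remains is that two definitions are in force, and that aligning the SAP with the protocol, the obvious way to reconcile them, would import the flaw.

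A reader might infer more: that the protocol withdraws everyone with resistance found on treatment and stops following them. The documents do not support this.

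- The sentence in protocol 1.3 names multidrug resistance, so it does not cover RR-TB alone.
- It sits in background text after the GeneXpert screening and susceptibility work-up, states no timing and does not mention follow-up.
- The two rules that end follow-up are confined to an MDR-TB initial isolate.

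No passage says that a patient who acquires resistance leaves follow-up, and none says that the patient stays. For toxicity, by contrast, protocol 8.3.3 and 8.5 state that follow-up continues.

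It is also fair that acquired resistance is not lost everywhere. The cure definition has no resistance exclusion, so a patient who is still culture-positive counts as not cured under secondary objective 5. Susceptibility testing is scheduled at end of treatment and at recurrence, so resistance can be tabulated. No primary or secondary objective compares acquired resistance directly.

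**Conclusion.** The concern holds in a limited form. The protocol's failure definition conditions objective 2.2.4 on a post-randomisation event that the regimens can cause, and it conflicts with SAP 6.7. Neither document says how RR-TB or MDR-TB found on treatment with a susceptible baseline isolate is to be classified, or what happens when that patient has no end-of-treatment culture.

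On assumed rates the protocol rule shrinks a 5.0-point difference to 3.2 points. On assumed counts it moves a p-value from 0.31 to 0.045. These figures show what the rule can do. They are not estimates for this trial and do not describe a literal SAP 6.7 analysis. The main calculation treats every on-treatment diagnosis as acquired; if half were missed at entry, the gap narrows to 4.1 against 3.2 points.

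The direct effect is on one secondary objective. The point should be corrected before analysis but does not threaten the primary comparison. Confidence is moderate, because the bias depends on which definition and which missing-data reading are applied.

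**What to change.** 1. **Protocol, definition of treatment failure.** Limit the exclusion to patients whose baseline isolate, or a retest of the stored baseline isolate, shows RR-TB or MDR-TB. Count RR-TB or MDR-TB diagnosed on treatment with a susceptible baseline isolate as failure in the randomised arm.
2. **SAP 6.7.** Use the same definition. State that these patients count as failures even if the end-of-treatment culture is missing, so that the missing-data rule in SAP section 5 does not remove them.
3. **Reporting.** Tabulate acquired resistance by arm.
4. **Withdrawal and follow-up.** Reconcile protocol 1.3 (multidrug resistance, no timing) with 8.2.3 and the section on withdrawal from the study (initial isolate only). State whether patients with resistance found on treatment remain in outcome follow-up. This point does not say which rule is right.

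**Cost.** Items 1 to 3 change wording in the failure definition and SAP 6.7 and add one table. Susceptibility testing is already scheduled at baseline, month 2, end of treatment and recurrence. Protocol 7.3.2 already stores culture-positive samples from baseline and from months 4 to 8. Retesting stored baseline isolates adds a small amount of laboratory work. The reported failure rate will rise slightly.

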### *Definition of treatment cure*

Patient whose baseline smear (or culture) was positive at the beginning of the treatment and is smear/ culture negative in the last month of treatment and on at least one previous occasion at least 30 days prior.

## **Discontinuation of study treatment**

The investigator may discontinue a patient from treatment in the event of a severe or serious adverse event, or at any time he/she thinks it's in the patient's best interest. If there is a medical reason for withdrawing study treatment, the patient will remain under the supervision of the investigator until satisfactory health has returned irrespectively of the reason for discontinuation. The frequency of patient review will be determined by the clinical need to ensure optimal care.

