### 8.3.3 Grade 3 and 4 Adverse Events

Any grade 3 or 4 event should be carefully assessed. The research clinician should rule out other possible causes of the symptoms before discontinuing study medication. When possible, concomitant medications should be with-held first at the discretion of the research clinician if causality is suspected. If after careful assessment and in the clinician's judgment the event is due to study drug(s), the causative study drug(s) may be withheld. The patient should be permanently discontinued from study medications if it is in their best interests to do so. Further treatment of the TB will be directed by the clinician in consultation with the investigator. The patient will continue to be followed according to the protocol. Other adverse events of any grade not thought to be due to the study drugs, should be managed at the discretion of the research clinician; study treatment should be continued, if possible.

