## 8.5 Safety Monitoring

### Procedures for assessing safety

At each clinic visit patients will be asked about changes (adverse events) that have occurred since their previous visit. Physical assessments will be performed at baseline and on subsequent scheduled visits.

Safety laboratory investigations will be performed at screening and in accordance with the schedule of evaluations, as well as determined by the study clinician based on the evaluation.

1. Screening tests and scheduled subsequent visits will include: Liver function, renal function, full blood count: At screening, baseline and every second month until Month 8 of follow up. Thereafter, tests will be performed at the end of TB treatment, time of TB recurrence and at the study termination visit.
2. 2. Pregnancy test: At screening, baseline and every month thereafter as per the SoE.

For isolated asymptomatic or symptomatic Grade 3 elevation of total bilirubin all medications should be discontinued and held for up to 14 days until levels and symptoms are Grade  $\leq 2$ , at which time therapy may be reintroduced. If there is  $\geq$  Grade 2 elevation of total bilirubin with transaminase elevation of grade  $\geq 3$ , this

should be treated as Grade 4. If Grade 3 toxicity develops after re-introduction of the study medications or if the Grade 3 toxicity does not resolve within 14 days, then the participant will be discontinued from study medications. The participant will continue to be followed on study, off study drugs. All medications may be restarted if the laboratory abnormalities were thought secondary to a concomitant illness.

Participants who develop Grade 4 elevations of the total bilirubin will be discontinued from study medications. The participant will continue to be followed on study, off study drugs.

Any additional test that the investigator deems necessary for the clinical evaluation of the subject can be performed.

Any adverse events detected will be graded according to a modified version of the toxicity criteria produced by the Division of AIDS and coded using MedDRA.

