### QTc Prolongation

Participants in this trial may receive Moxifloxacin which has the potential to prolong the QTc interval. All QTc measurements will be corrected with the Fridericia correction.

The protocol-specific criteria for grading prolonged QTc are as follows:

PARAMETER	GRADE 1 MILD	GRADE 2 MODERATE	GRADE 3 SEVERE	GRADE 4 POTENTIALLY LIFE- THREATENING
Prolonged QTc (using Fridericia QT correction formula)	Asymptomatic, QTc interval 0.45 – 0.47 sec	Asymptomatic, QTc interval > 0.47- < 0.50 sec	Asymptomatic, QTc interval $\geq$ 0.50 sec OR a QTc > 0.48 sec with an increase in interval $\geq$ 0.06 sec above baseline	Life threatening consequence, eg, Torsade de pointes or other associated serious ventricular dysrhythmia

If Grade 2 QTc prolongation develops during the course of the study and is felt to be due to study medications, the participant will be monitored more closely, with twice weekly visits and QTc evaluation. If Grade 3 QTc prolongation occurs, all study drugs will be discontinued and the participant will be referred to hospital for further assessment and management. If the QTc prolongation is considered most likely to be due to concomitant illness or medication, standard management, including discontinuation of the likely causative agent, should be undertaken.

If a participant develops Grade 4 QTc prolongation, he or she will be hospitalized and discontinued from study medications. If the prolongation is felt to be caused by a concomitant medication and resolves with discontinuation of that agent, study medications may be restarted. Otherwise, the participant will be referred to the NTP for treatment of his or her TB according to local standards of care. The participant will continue to be followed on study, off study drugs.

Serious adverse events will be reported to the MCC and the UKZN Biomedical Research Ethics Committee. (BREC) according to their specific requirements.

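### The protocol is inconsistent on whether outcome follow-up continues after study drugs stop, and silent on it after a protocol violation, although the SAP's ITT analysis depends on it

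*Protocol*

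**What the plan says.** Several protocol sections deal with follow-up once study drugs are stopped.

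- Section 8.3.3, for Grade 3 and 4 events judged due to study drug: "The patient will continue to be followed according to the protocol".
- Section 8.5, for Grade 4 bilirubin elevation and for Grade 3 toxicity that persists or returns: "The participant will continue to be followed on study, off study drugs". The QTc section repeats this for Grade 4 prolongation.
- The QTc section, for Grade 3: "If Grade 3 QTc prolongation occurs, all study drugs will be discontinued and the participant will be referred to hospital for further assessment and management". It does not say whether study follow-up continues.
- Discontinuation of study treatment, which covers severe or serious adverse events and any stop the investigator judges to be in the patient's interest: where the reason is medical, the patient stays under supervision until health is satisfactory, and "The frequency of patient review will be determined by the clinical need to ensure optimal care". Scheduled cultures and recurrence visits are not mentioned.

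On leaving the study, Withdrawal from the study says: "Patients withdrawn from study due to a protocol violation will be included in the safety database of the study". It does not define which violations lead to withdrawal. The same section ends follow-up for two groups identified from initial specimens: "Patients withdrawn from study because their initial TB isolate is found to be MDR –TB will not be followed up further" (unless safety requires it), and "patients withdrawn from study because their initial cultures are negative do not need to be followed up further" (unless an adverse event is ongoing).

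SAP section 4 puts all primary analyses on an ITT basis and defines the set: "This population consists of all participants enrolled and randomised to the intervention and control arms". It then removes people found ineligible on pre-randomisation criteria and people with no post-randomisation visit and no data. SAP section 5 ignores missing data, as missing at random, unless potentially biasing patterns are identified. SAP section 6.3 requires two negative cultures at different visits for conversion.

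**The concern.** An ITT comparison needs outcomes from randomised patients whether or not they stay on drug. The SAP relies on this: its per-protocol set is formed by removing data collected after a long treatment interruption, so the ITT set is meant to contain such data. A site that follows the discontinuation section literally could see a patient only until the adverse event resolves, and collect no month 6 culture or recurrence assessment. A site that follows 8.3.3 would collect both.

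The trial is open label, so decisions to stop drugs or to withdraw a patient for a violation are made with the arm known. Moxifloxacin is the drug that the protocol lists with QT prolongation, and Grade 3 QTc stops all study drugs. Loss of outcomes could therefore differ by arm and be related to prognosis. The SAP has no rule for a participant who lacks the two cultures, so under its default such losses pass into the primary estimate. Cultures that were never taken cannot be recovered at analysis.

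**Working it through.** **The plan's own figure.** Protocol 9.1 uses 75% v 60%, two-sided 0.05, 80% power and a continuity-corrected chi-square test.

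- Uncorrected: n = [1.96·√(2·0.675·0.325) + 0.8416·√(0.75·0.25 + 0.60·0.40)]² / 0.15² = 151.9, so 152 per arm.
- Corrected: n/4·[1 + √(1 + 4/(n·0.15))]² = 164.9, so 165 per arm and 330 in total. The stated size is reproduced exactly.
- It holds no allowance for lost outcomes. If 10% are lost at random and dropped (148.5 per arm), corrected power falls from 80.0% to 75.3%.

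**Bias from selective loss.** The documents give no stopping rates, no conversion rate in stoppers and no share of stoppers who lose the outcome. The following are assumptions.

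- Patients who stay on drug convert at p = 0.75 (intervention) or 0.60 (control), the rates in 9.1.
- A share d stops, and stoppers convert at 0.6p.
- A share f of stoppers loses the outcome and is dropped.

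True rate = p·[(1 − d) + 0.6d]. Observed rate = p·[(1 − d) + 0.6d(1 − f)] / (1 − f·d).

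For d = 10% v 2%, the true rates are 0.75·0.96 = 0.720 and 0.60·0.992 = 0.595, a difference of 12.5 points.

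- f = 1: observed 0.750 − 0.600 = 15.0 points.
- f = 0.5: observed 0.6975/0.95 − 0.5916/0.99 = 0.734 − 0.598 = 13.7 points.

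| Stop, intervention v control | Stoppers losing outcome | True difference | Observed | Bias (points) |
|---|---|---|---|---|
| 10% v 2% | all | 12.5 | 15.0 | +2.5 |
| 10% v 2% | half | 12.5 | 13.7 | +1.2 |
| 6% v 2% | all | 13.7 | 15.0 | +1.3 |
| 2% v 10% | all | 16.8 | 15.0 | −1.8 |
| 2% v 10% | half | 16.8 | 16.0 | −0.8 |

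If no stopper loses the outcome (f = 0), the bias is zero. For scale, the standard error of the planned difference is √[(0.1875 + 0.24)/165] = 5.1 points.

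**Outer bound.** Suppose both arms truly convert at 60%, and 10% of the intervention arm is lost, all of them non-converters. That arm then shows 0.60/0.90 = 66.7%, and the chance of a two-sided p < 0.05 is about 23% instead of 5% (uncorrected normal approximation). This is a limit, not an expectation.

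**The case against.** The discontinuation section can be read as a duty of care that runs alongside the visit schedule. It sets how often a patient is reviewed clinically and says nothing about leaving the study. The explicit toxicity rules point the other way: 8.3.3, bilirubin and Grade 4 QTc all continue follow-up, and 8.3.3 on a fair reading also reaches Grade 3 QTc when judged drug-related. A reader might infer that the protocol plans to stop cultures once drugs stop. The documents do not say that.

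A reader might also infer that violators are kept for safety alone. The text says they are included in the safety database; it does not say only. The SAP keeps randomised participants with data and uses all their non-missing time points, so cultures already taken are not discarded. Its missing-data default carries a qualifier for biasing patterns, although no method is attached.

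Nor is a bias toward moxifloxacin established. Ethambutol has its own listed toxicity, so which arm stops more is not known. Section 8.1 describes a drug substitution for QT prolongation where the QTc section stops all study drugs at Grade 3. Those passages need reconciling too, and they leave the frequency of stopping uncertain. Cultures at weeks 2, 4 and 6 and month 2 may already show conversion in many stoppers, so the month 6 and recurrence outcomes are more exposed than the end of the intensive phase.

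All of this limits the claim without removing it. Sections 8.3.3 and Discontinuation of study treatment cover overlapping patients with different follow-up wording. No continuation rule clearly covers a stop made on the investigator's judgement of best interest, or a change of therapy for a positive smear (8.2.2). The note under Table 5 lets procedures be omitted when clinically not required. Nothing says that outcomes are still sought from a patient withdrawn for a violation.

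**Conclusion.** The point holds as an internal inconsistency and a gap, not as a plan to stop outcome collection. Following the discontinuation and withdrawal sections as written permits outcome loss after randomisation that may depend on arm, which conflicts with the SAP's ITT analysis and its missing-data default.

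The size cannot be derived from the documents. Under the assumed 10% v 2% stopping and 0.6 relative conversion, the bias is 1.2 to 2.5 points as the share of stoppers losing the outcome goes from half to all. That is a quarter to a half of the standard error of the planned difference. It is smaller if follow-up mostly continues, and it changes sign if control patients stop more often. The sample size of 330 is not in error.

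The withdrawals for initial MDR-TB and negative initial cultures are a separate matter. They rest on baseline specimens and are less prone to arm-related bias. However, the SAP's ITT definition does not name either group, and its ineligibility clause does not clearly reach them: section 4.1 requires a positive smear rather than a positive culture, and section 4.2.4 concerns resistance known at screening.

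**What to change.** In the protocol, reconcile 8.3.3, 8.5, QTc Prolongation (including Grade 3), Discontinuation of study treatment and Withdrawal from the study around one statement:

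- Stopping or changing study drugs, or a protocol violation, does not end the smear, culture and recurrence assessments in Table 5.
- Reviews needed for clinical reasons are additional to that schedule.
- Protocol violation is removed as a reason to end study follow-up.
- The stated exceptions are withdrawal of consent and the existing withdrawals for initial MDR-TB and negative initial cultures.

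In the SAP, section 4 should state how the MDR-TB and culture-negative patients enter the ITT set.

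The cost is a wording amendment and a small number of off-treatment visits and cultures that are already in the schedule. No treatment or stopping rule changes.
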